# A Multi-Center Study on the Utility of Non-invasive Carboxyhemoglobin and Total Hemoglobin Measurement in Emergency Department Patients

## SUNE0002 version 3

---

### 1 INTRODUCTION

This document is a protocol for a clinical research study sponsored by Masimo Corporation. The study will be conducted in compliance with the ethical principles that have their origin in the Declaration of Helsinki. In participating in the study, the Investigator agrees to adhere to all stipulations of this protocol, the conditions of IRB/IEC approval, ISO-14155, and International Conference on Harmonization Good Clinical Practice guidelines ICH GCP.

#### 1.1 Background and Rationale

Carbon monoxide (CO) is the leading source of poisoning in the US and elsewhere. CO poisoning (COP) can cause severe disability and death. CO is released whenever there is combustion of fossil fuels including wood, oil, kerosene, etc. The diagnosis of COP is made when exposure to CO occurs and there are signs and symptoms consistent with toxicity. Exposure can be determined either with measurement of environmental CO levels or carboxyhemoglobin (COHb) concentrations in the blood. COP can cause headache, nausea, vomiting, dizziness, syncope, loss of consciousness, coma, focal neurological deficits, psychiatric manifestations and cardiac ischemia. Because CO is colorless, tasteless and has no odor, patients may not know if they have been exposed. Universal screening with a blood test is not feasible and not typically performed. Many of the signs and symptoms associated with COP are non-specific and may be attributed to other conditions if CO exposure is not considered. Patients could therefore be released from the hospital to return to an environment with CO potentiating toxicity, leading to death or severe disability. The use of environmental CO detectors has increased in public facilities and private homes in the US, but screening of emergency medicine subjects for CO exposure is not yet a standard practice. A device which estimates COHb concentrations non-invasively using a finger probe has been approved by the FDA and utilized in clinical care. This device passes 8 separate frequencies of light through the fingertip and measures absorbance at those frequencies during pulsatile blood flow, allowing estimation of pulse oximetry (Sp) hemoglobin species (Oxyhemoglobin: SpO2, total hemoglobin: SpHb, carboxyhemoglobin SpCO, and methemoglobin: SpMet). We have used this device at Rhode Island Hospital to screen patients who presented for any complaint and showed that 1-4/10,000 patients had unsuspected (both to the patient and clinician) COP. The sources of exposure were often faulty exhaust systems or dysfunctional appliances in the home. Other investigators have replicated these findings in Vermont (unpublished), Europe and Turkey. Studies which have evaluated the accuracy of the device when compared to blood COHb measurements have shown variable results. Taken together, these studies show that sensitivity of the device has utility for COP screening, but it does not have the accuracy to replace blood COHb.

The device manufacturer has developed a new diagnostic platform that allows for simultaneous measurement of SpO2, SpCO and SpHb, with modifications that may improve diagnostic performance. Most emergency department routinely measure SpO2 during triage, and some (such as Rhode Island Hospital) also measure SpCO. Enhancement of the triage oxyhemoglobin profile to include total Sp CO and SpHb could provide significant benefit in a busy emergency department setting.

Determination of anemia rapidly in the Emergency Department may prevent morbidity and mortality. Patients with traumatic injuries causing hemorrhage, occult internal hemorrhage (GI bleeding, ectopic pregnancy, etc.), hemolysis, or other critical anemias, could be quickly identified. Triage nurses could then expedite physician evaluation and acquisition of blood samples for type and cross. Screening for anemia is subjectively performed by observing for pallor in the skin and mucous membranes (in particular, the palpebral conjunctiva). However, studies have shown that this method is not reliable. Validation of a non-invasive screening method that may be utilized in the pre-hospital setting or in emergency department triage could prevent complications associated with delays in diagnosis of anemia by blood analysis.

### 1.2 Study Device

SpHb and SpCO technology uses a multiwavelength sensor with various light emitting diodes (LEDs) that pass light through the measurement site to a detector as shown in the figure below. Signal data is obtained by passing various visible and infrared lights (LEDs, 500 to 1400nm) through a capillary bed (for example fingertip) and measuring changes in absorption during the blood pulsatile cycle. The detector receives the light and converts it to an electrical signal which is, in turn, used to predict SpHb and SpCO.

[figure not shown]

Figure 1 Masimo technology overview

Devices used for SpHb and SpCO measurement evaluation consist of a Masimo Rainbow pulse CO-oximeter (e.g. Masimo Rad-67, investigational) connected to a fingertip sensor (e.g., Masimo DCI Mini Super sensor, investigational). The investigational devices used in this study employ similar material and technology compared to FDA-cleared devices. The investigational devices have undergone risk analysis and safety testing in accordance with applicable safety standards, including electrical safety, current leakage, mechanical safety and biocompatibility testing for patient contacting materials. That risk assessment concluded that the investigational devices do not pose unmitigated risks to operator or subject.

The Rad-67 is a prototype handheld pulse CO-oximeter with Rainbow technology similar to already cleared Masimo noninvasive pulse CO-oximeters and is intended for spot-check measurements on patients in various care area settings (hospitals, hospital-type facilities, and clinics). The device is a more compact version of 510(k) cleared Rad-57 and Pronto devices. The Rad-67 also comes with an upgraded display with touchscreen capabilities. The Masimo Rad-67 is intended to be used with Masimo sensors and patient cables.

---

# A Multi-Center Study on the Utility of Non-invasive Carboxyhemoglobin and Total Hemoglobin Measurement in Emergency Department Patients

## SUNE0002 version 3

---

The Masimo reusable DCI Mini sensor is intended to measure non-invasive physiological parameters such as SpO2, SpHb, SpCO, SpMet, PR, and PI, similar to the existing FDA cleared Masimo reusable sensors. The DCI Mini sensor has a slimmer and more compact design compared to other Masimo reusable finger sensors. The DCI Mini sensor is intended to be used on adults or pediatric subjects weighing greater than 3 kg.

### 1.3 Risk/Benefits

**Benefits:** There is no specific benefit to the individual for participation in this research study.

**Sensor risks:** Pulse CO-oximeter noninvasive measurement uses wavelengths in the red and near infrared range like a conventional pulse oximeter used in routine clinical practice for over 15 years. The additional LEDs from Rainbow sensors have been tested and meet the Exempt classification for photo-biological safety of light sources.

All patient-contact materials have been subjected to biocompatibility tests per ISO 10993-1 and results demonstrate that the materials are non-toxic, non-irritating, and non-sensitizing. The sensors have been subjected to performance, mechanical, and electrical testing and results demonstrate that the sensors meet the requirements for safety and effectiveness for the intended use of the product.

## 2 STUDY OBJECTIVES

The purpose of this study is to determine the clinical utility of triage screening for anemia and COP in the ED setting.

### SpCO:

1. Measure extent of agreement between SpCO and COHb determined by co-oximeter measurement of blood in the emergency department.
2. Determine diagnostic performance characteristics of SpCO (sensitivity, specificity, False Positive and False Negative) compared to gold standard of laboratory measurement of COHB in whole blood using a co-oximeter. We will define *a priori* a “true positive” of COHb  $\geq 7$  for COP.
  - a. We will also dichotomize smokers and non-smokers, and perform a post-hoc analysis to determine if the use of an alternate threshold for “true positive” based on smoking history is feasible.
3. Determine utility of SpCO for screening purposes by surveying the provider to determine the impact of screening test. Providers will be asked: Did the patient have a CO poisoning clinical diagnosis? Did SpCO screening lead to identification of occult toxicity?
4. Determination of elimination pharmacokinetics of CO in emergency department patients with CO toxicity as related to method of O2 administration (nasal cannula, non-rebreather mask, CPAP, or endotracheal intubation). Clinicians will administer O2 as dictated by patient care, the method and amount of O2 will be recorded. CO elimination will be evaluated as a function of FiO2.

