### 5 SUBJECT SELECTION AND WITHDRAWAL

#### 5.1 Number of Subjects

At least 3000 subjects across three sites may be enrolled onto this study. We expect to enroll approximately 1000 subjects at each site. This sample size is based on previous experience that has have demonstrated: 1) Occult toxicity occurs in approximately 1-3/10,000 ED visits. 2) Higher numbers of CO, needed to determine extent of agreement between non-invasive and laboratory measurements, are infrequent.

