### 5.4 Study Timelines

Subject participation in this study is not expected to delay any care or prolong their stay in the ED. The study will be conducted approximately between October 1, 2016 and December 31, 2018. We anticipate enrolling an average of 10 patients a day.

**Subject Recruitment** Patients may be screened at triage with FDA approved oximeter devices as part of standard of care procedures. The results of this screening will be recorded in the chart if performed, by clinical staff as per routine procedure.

A convenience sample of patients aged 1 year and up presenting to the emergency department for any complaint and who have received or will receive a blood test for CBC or an IV catheter during their care (determined by their care provider independently) or will be approached by trained research staff for evaluation for enrollment in the study.

We will also approach patients with known CO exposure or who have anemia to enroll them in this study. The attending emergency physician will conduct usual clinical care; research staff will seek to obtain informed consent for this part of the study.

Research staff will also be notified of any patient presenting to the emergency department with suspected CO exposure (e.g. rescued from fire), toxicity or anemia, or patients with signs and symptoms of CO toxicity (unexplained headache, nausea, vomiting, dizziness or lightheadedness, syncope, neurological deficits, shortness of breath). The treating provider will be notified if the patient has agreed to participate. If the clinician determines an IV is necessary, these patients will also be eligible for inclusion in the study.

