# A Multi-Center Study on the Utility of Non-invasive Carboxyhemoglobin and Total Hemoglobin Measurement in Emergency Department Patients

## SUNE0002 version 3

---

recorded on the case report forms (CRF). Demographic information, height, weight, gender, age, skin color, vital signs (heart rate, blood pressure, respiratory rate, pulse oximetry), presence or absence of jaundice, smoking history will be recorded on CRFs along with the values of SpCO, SpHb, COHb and hemoglobin concentration. If an abnormal COHb (>10%) value is observed, the measurement will be repeated using a Masimo FDA-cleared pulse CO-oximeter (e.g. Rad-57 and DCI sensor). If abnormal values are confirmed, the patient's clinician will be notified by research staff immediately. The clinician will independently determine any course of action related to patient care utilizing this information. CRFs will be kept within a locked filing cabinet in the Emergency Medicine Research Office which is locked. A de-identified data spread sheet will be created and kept on a storage device with encryption.

Stage 2: We will also approach patients with known CO exposure or who have anemia to enroll them in an arm of this study. Research staff will be notified of any patient presenting to the emergency department with suspected CO exposure or toxicity including patients with signs and symptoms of CO toxicity (headache, nausea, vomiting, rescued from fire, unexplained neurological deficits) or who have low hemoglobin values for any reason determined as part of their routine care. The treating provider will be notified if the patient has agreed to participate and if the clinician determines an IV is necessary, these patients will also be eligible for inclusion in the study.

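### SpCO accuracy from a CO-enriched study is not split by recruitment stage or projected to a triage prevalence, so raw false-positive and true-positive counts can flatter screening

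*Combined protocol and SAP*

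**What the plan says.** Section 2 gives the purpose as "to determine the clinical utility of triage screening for anemia and COP in the ED setting". SpCO item 2 of that section will "Determine diagnostic performance characteristics of SpCO (sensitivity, specificity, False Positive and False Negative) compared to gold standard", with the reference side fixed in advance as "a “true positive” of COHb" at 7 or more. Item 2 lists no predictive value or likelihood ratio, gives no SpCO cut-off, and does not name the subjects who enter the analysis.

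Recruitment has two sources. Section 5.4 describes "A convenience sample of patients aged 1 year and up presenting to the emergency department for any complaint" who have had or will have a CBC or an IV catheter. Section 7, Stage 2 adds: "We will also approach patients with known CO exposure or who have anemia to enroll them in an arm of this study". Suspected exposures, such as people rescued from a fire, are also referred to research staff. The expected number of such patients is not stated.

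Two rates appear, neither applied to the accuracy result. Section 1.1 reports that "1-4/10,000 patients had unsuspected (both to the patient and clinician) COP", and section 5.1 says "Occult toxicity occurs in approximately 1-3/10,000 ED visits" as part of the sample-size rationale.

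Utility is also addressed by a provider survey (SpCO item 3). Under section 7 that survey covers patients who end up with a diagnosis of CO poisoning or anemia.

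**The concern.** A screening test is judged by what happens to the people who test positive. In a sample to which exposed patients have been added, the balance of false to true positives reflects how many of them were recruited. A 2x2 table from such a sample could show few false positives per true positive and be read as support for triage screening, although the same device would produce many more at triage. The survey would not correct this reading, because false alarms in patients who never receive a diagnosis fall outside it.

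The misreading has a practical consequence. Section 7 says that if clinical utility is shown, Stage 1 data will be unmasked and subjects with high device readings contacted. The supplied text does not say which result would show utility.

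**Working it through.** **Inputs from the protocol.** Unsuspected CO poisoning 1-4 per 10,000 (section 1.1) and occult toxicity 1-3 per 10,000 (section 5.1); at least 3000 subjects (section 5.1); reference positive COHb of 7 or more (section 2).

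**Assumptions, because the protocol gives no figures.** Sensitivity (Se) 80-90%; specificity (Sp) 95-99%; share of the enrolled sample with COHb of 7 or more, 2-5%; prevalence of COHb of 7 or more among ED patients, 1%, for illustration.

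**The plan's own figure.** About 1000 subjects at each of three sites gives 3 x 1000 = 3000. No expected accuracy or precision target is given, so there is no statistical calculation to reproduce.

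**Step 1: where the positives would come from.** Expected occult cases among 3000 subjects not selected for CO exposure are 3000 x 0.0001 = 0.3 to 3000 x 0.0004 = 1.2. The chance of at least one is 1 - (1 - p)^3000, which is 26% to 70%. Apart from smokers and other incidental Stage 1 subjects with COHb of 7 or more, the positives behind the sensitivity estimate must come largely from patients recruited for exposure.

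**Step 2: a ratio that needs no accuracy assumption.** False positives per true positive = [(1 - Sp)/Se] x [(1 - p)/p]. For fixed Se and Sp only the second factor changes:
- p = 5%: 0.95/0.05 = 19
- p = 2%: 0.98/0.02 = 49
- p = 4/10,000: 0.9996/0.0004 = 2499
- p = 1/10,000: 0.9999/0.0001 = 9999

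The smallest change is 2499/49 = 51-fold and the largest is 9999/19 = 526-fold.

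**Step 3: predictive values.** PPV = Se x p / [Se x p + (1 - Sp)(1 - p)]. Each cell gives PPV, then false positives per true positive.

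| Prevalence | Se 80%, Sp 95% | Se 90%, Sp 99% |
|---|---|---|
| 1/10,000 (section 1.1) | 0.16%; 625 | 0.89%; 111 |
| 4/10,000 (section 1.1) | 0.64%; 156 | 3.5%; 28 |
| 1% (assumed) | 13.9%; 6.2 | 47.6%; 1.1 |
| 2% (assumed) | 24.6%; 3.1 | 64.7%; 0.54 |
| 5% (assumed) | 45.7%; 1.2 | 82.6%; 0.21 |

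Example: 0.80 x 0.0001 / (0.80 x 0.0001 + 0.05 x 0.9999) = 0.00008/0.050075 = 0.16%.

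Per 10,000 screened at 1-4/10,000, false positives number about 100 (Sp 99%) to 500 (Sp 95%), against 0.8 to 3.6 true positives.

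**Step 4: limit on the fold change.** The 51-fold minimum applies to false positives per true positive, not to PPV. The smallest PPV ratio is 64.7/3.5, about 19-fold.

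**The case against.** The strongest reply is that the listed measures are not wrong. Sensitivity and specificity do not change with prevalence as such. False positive and false negative, listed beside them, can be read as rates with the same property. No predictive value is planned, so harm arises only if someone derives one from the counts. This stands: a reader might infer that the planned results will overstate utility, but the documents support only that raw counts can be misread that way. Enrichment can also shift sensitivity through case spectrum, since known exposures may be more severe.

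A reader might also infer that Stages 1 and 2 are to be pooled. The protocol does not say so. It calls Stage 2 an arm and refers to Stage 1 subjects separately. What can be said is that the analysis set is left open.

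Third, 1-4/10,000 is the rate of unsuspected poisoning, which is narrower than COHb of 7 or more. Known exposures also arrive at triage, and SpCO item 2a foresees that smokers may need another threshold. The protocol gives no ED prevalence for COHb of 7 or more. It therefore does not follow that nearly every reading above the cut-off would be false against the item 2 reference: at an assumed 1%, PPV is about 14-48%. This stands, and it is why both target conditions must be shown.

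Fourth, Stage 1 is a convenience sample of patients having a CBC or IV, so its specificity may differ from that of all triaged patients. This is a caveat to report. Stage 1 remains a better source of specificity than patients recruited for exposure.

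Finally, the text supplied for review omits the part between sections 3 and 5, so absence of a projection is judged on what remains.

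**Conclusion.** The point holds in a limited form, as a cheap improvement. The accuracy objective stops one step short of the screening question in section 2: it neither names the stages analysed nor carries the result to a triage prevalence, and the survey does not fill the gap.

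The 51- to 526-fold change in false positives per true positive depends on the assumed 2-5% sample prevalence and on fixed accuracy, but not on what that accuracy is. The PPV of 0.16-3.5% for unsuspected poisoning also depends on the assumed sensitivity and specificity, and on accuracy measured against COHb of 7 or more carrying over to that narrower condition. The documents do not show that the planned analysis is biased or that the device would fail as a screen.

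**What to change.** In SpCO item 2 of section 2:

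(a) Report accuracy separately for Stage 1 and Stage 2. Take specificity and the false-positive rate from Stage 1 subjects not recruited for CO exposure, noting that they are a convenience sample having a CBC or IV.

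(b) Add one table, at a stated SpCO cut-off and with confidence intervals, giving PPV, negative predictive value, false alarms per 10,000 screened and false alarms per case. Show it at the Stage 1 prevalence of COHb of 7 or more and, for unsuspected poisoning, over 1-4/10,000. State that sensitivity comes largely from known or suspected exposures and may not carry over to occult cases.

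(c) Do not use the ratio of false to true positives from a pooled Stage 1 and Stage 2 sample as evidence of screening utility.

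The cost is one extra table. SpCO, COHb and smoking history are already on the case report form; the recruitment stage must be identifiable for each subject. The screening figure will be less favourable, and specificity will rest on somewhat fewer subjects.

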### SpHb :

#### Primary objectives

1. Determine diagnostic performance characteristics of SpHb for detecting anemia (Sensitivity, Specificity, False Positive and False Negative) compared to reference hemoglobin measurement by the hospital laboratory, based on WHO criteria for anemia. For comparison, total Hb determined by blood gas analyzer will also be measured and used only related to research. This value will be not recorded in the medical record and will be kept blinded to clinical care team. This will be completed if sufficient number of participants with anemia are enrolled during the study period. (If not, a separate study related to this objective will be designed)
2. Determine utility of SpHb for screening purposes
  - a. Establish threshold of SpHb that best predicts the clinical outcome of “acute treatment of anemia”, defined as: blood transfusion, admission to hospital for further workup of anemia, or admission to operating room

---

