#### 5.2 Inclusion Criteria

- Age 1 year or older.
- At least one digit has acceptable width as measured by study-provided digit gauge.
- Presenting to emergency department for any complaint.
- Potential for IV catheter and/or blood draw for CBC as standard of care.

---

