## **7 STUDY PROCEDURES**

Stage 1: After obtaining informed consent, from the patient (18 y.o. and over), legal guardian (<18 y.o.) with child assent or patient surrogate, as appropriate, the sensor will be placed as per sensor directions for use (DFU), and the SpCO and SpHb values recorded (this process takes less than 1 minute and is not associated with any pain or discomfort). Near-simultaneously (██████████), a █ ml vial of blood will be withdrawn from the patient's IV site for analysis. No new needle sticks will be performed. The study will not interfere with any aspects of patient care. The blood analysis for COHb will be performed immediately in the ED using a blood gas analyzer specifically obtained and properly calibrated for this study, by research personnel who will receive a standardized training program on its use. The patients will incur no additional cost and they will experience no delay in care or any prolongation of their stay in the ED stay related to this study. Hospital Laboratory Hemoglobin values, if measured as part of patient care, will be obtained from the patient's chart and

---

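### The research analyzer Hb is withheld from the care team with no critical-value exception, and for a few IV-only subjects it may be the only blood Hb

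*Combined protocol and SAP*

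**What the plan says.** **Blinding.** Section 2, SpHb primary objective 1, has a total Hb measured on the blood gas analyzer for research comparison only and adds: "This value will be not recorded in the medical record and will be kept blinded to clinical care team". It states no exception. The reference for this objective is the hospital laboratory Hb.

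**Entry without a CBC.** Section 5.2 requires "Potential for IV catheter and/or blood draw for CBC as standard of care". Section 5.4 describes the convenience sample as patients "who have received or will receive a blood test for CBC or an IV catheter during their care". Under either wording an IV alone is enough.

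**Laboratory Hb is conditional.** Section 7, Stage 1: "Hospital Laboratory Hemoglobin values, if measured as part of patient care, will be obtained from the" chart. No study procedure requires one.

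**The COHb rule.** Section 7, Stage 1, says "The blood analysis for COHb will be performed immediately in the ED using a blood gas analyzer". It then provides: "If an abnormal COHb (>10%) value is observed, the measurement will be repeated" on a cleared pulse CO-oximeter, and "If abnormal values are confirmed, the patient's clinician will be notified by research staff immediately". After that, "The clinician will independently determine any course of action related to patient care utilizing this information".

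**Other places where an Hb rule might sit.** The end-of-study contact at the close of Section 7 concerns high CO readings only. The visible text of Section 8 has no Hb notification rule.

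**The concern.** The protocol measures two blood quantities for research in the same ED setting. For COHb, a dangerous confirmed value goes to the clinician immediately. For Hb, the rule is to withhold, with no floor.

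If a laboratory Hb exists, withholding costs the patient little, because the clinician has the reference measurement. If none exists, research staff may hold a critically low blood Hb that the clinician lacks and has no particular reason to seek. Section 1.1 argues that rapid recognition of anemia in the ED can prevent harm, and one secondary objective asks whether screening found occult anemia. An unsuspected low Hb is therefore within what the study expects to meet.

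Staff judgment does not fully close the gap. Disclosing the value would depart from the blinding rule, and Section 8.4 wants sponsor and IRB approval before a deviation is initiated.

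What is at stake is the safety of individual subjects, not the validity of an estimate.

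**Working it through.** The plan states no figure on this point, so the check is mainly a reading of the text.

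**Step 1: can a subject have an analyzer Hb and no laboratory Hb?** Entry needs a CBC or an IV (Sections 5.2, 5.4), the research sample comes from the IV site (Section 7), and laboratory Hb is taken from the chart only if it exists (Section 7). Yes.

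**Step 2: which subjects?**

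| Group | Clinical Hb assured? | Can the gap apply? |
|---|---|---|
| Stage 1, CBC ordered | Expected | Generally no |
| Stage 1, IV only | No | Yes |
| Stage 2, anemia | Yes; recruited on a low routine-care Hb | Generally no |
| Stage 2, CO exposure, IV only | No | Yes |

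**Step 3: immediate alert rules for research blood values in the visible text.** COHb: 1. Hb: 0.

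**Step 4: is the Hb known during the visit?** Section 7 says the COHb analysis is done at once in the ED. Section 2 has the research Hb also come from a blood gas analyzer. That both are read together is a reasonable inference, but the text does not state it for Hb.

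**Step 5: scale.** Planned enrollment is 3 sites × 1,000 = 3,000 (Section 5.1). The documents give neither the share *f* of subjects with an IV and no laboratory Hb nor the rate *p* of critically low Hb among them. Both ranges below are assumptions.

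- Subjects without a laboratory Hb: n = 3,000 × f
- Expected critical values: n × p
- Probability of at least one: 1 − (1 − p)^n

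| f | p | n | Expected | P(at least 1) |
|---|---|---|---|---|
| 1% | 0.1% | 30 | 0.03 | 0.03 |
| 5% | 0.5% | 150 | 0.75 | 0.53 |
| 10% | 0.5% | 300 | 1.5 | 0.78 |
| 20% | 1% | 600 | 6 | 0.998 |

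The spread shows that the number cannot be pinned down; no row is a best estimate.

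**Step 6: effect of a narrow alert on the threshold analysis.** The derivation and validation sets are 3 × 500 = 1,500 each (Section 2, SpHb primary objective 2). On the same assumptions and an even split, alerts per set run from 0.03 ÷ 2 = 0.015 to 6 ÷ 2 = 3, and 3 ÷ 1,500 = 0.2%. The expected number of acute-treatment events is not given, so the share of events cannot be calculated.

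**The case against.** **The harm needs several conditions at once.** The subject must be IV-only, get no CBC at any point in the visit, be critically anemic, and have the analyzer Hb read in time. Providers decide independently whether to order a CBC, so critical anemia may be uncommon among those without one. Usual care is not reduced, and a CBC can still be ordered later. This stands, and it is why the point is minor.

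**The COHb parallel is imperfect.** Section 1.1 describes CO as occult and not routinely tested in blood, whereas Hb is part of ordinary ED care. ED co-oximetry is the reference for COHb; the analyzer Hb is only a comparator. The COHb alert also waits for confirmation. These differences are real. They weaken the precedent but do not justify silence where no laboratory Hb exists. A repeat on a pulse device would not suit Hb, since SpHb is the test under study. The natural confirmation is the laboratory Hb, which the clinician must order.

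**Blinding protects the endpoint.** Transfusion and admission for anemia are clinician decisions that an alert could influence, and an alert would prompt laboratory Hb selectively in low-Hb subjects. This stands against a broad alert. One covering every subject below a threshold would include the anemic patients recruited on purpose, whose Hb clinicians already know; it would add endpoint influence for little safety gain. Restricted to subjects with no laboratory Hb resulted or ordered, the objection largely falls away: unless a test is ordered later, they cannot contribute to primary objective 1 at all.

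**A rule may lie elsewhere.** Consent pages and some text were removed or redacted, so this cannot be excluded.

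**Conclusion.** The point holds in a limited form. As written, the protocol can require a critically low analyzer Hb to be withheld from the clinician of a subject who has no other blood Hb. Those affected are mainly Stage 1 subjects, plus IV-only CO-exposure subjects. Their number cannot be quantified from the documents and may be very small or zero. The conclusion assumes that the analyzer Hb is read during the visit and that no rule sits in unseen text.

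Three stronger readings are tempting, and the documents do not support them:

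- A reader might infer that the blinding biases the results. It does not; the laboratory Hb is the reference, and no estimate is distorted by withholding the comparator.
- A reader might infer that anemic subjects in general are left unprotected. Stage 2 anemia subjects enter on a low Hb already known from routine care.
- A reader might infer that SpHb is withheld too. The blinding sentence covers only the analyzer value. The provider surveys suggest SpHb may reach clinicians, while the end-of-study unmasking of Stage 1 data suggests it may not. The text leaves this unclear.

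This is a minor subject-safety improvement that is cheap to make, not an error in the analysis.

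**What to change.** Amend SpHb primary objective 1 and Section 7 as follows.

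- **Trigger:** only when no hospital laboratory Hb has resulted or been ordered, and the analyzer Hb is below one prespecified critical threshold. Agree the threshold with site clinicians and IRBs, bearing in mind that entry starts at age 1 year.
- **Action:** research staff tell the treating clinician at once that an unconfirmed research Hb is critically low and that a laboratory Hb should be considered. The clinician decides independently. The value stays out of the record, and blinding is unchanged for all other subjects.
- **Status:** state that the analyzer Hb is read with the COHb during the visit, and that the alert is protocol procedure and not a deviation under Section 8.4.
- **Data:** record the alert and its time on the CRF.
- **Analysis:** keep alerted subjects in the main acute-treatment analysis, report their number, and add a sensitivity analysis excluding them from both the derivation and validation sets. Repeat the primary objective 1 accuracy analysis without subjects whose laboratory Hb was ordered after an alert.

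**Cost:** a protocol amendment with IRB approval, one agreed threshold, one CRF entry and two short sensitivity analyses. No study procedure is added. A few clinician-ordered laboratory tests may follow, and the Section 7 statement that patients bear no extra cost should allow for them.

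**Downside:** the alert may influence treatment in the few alerted subjects. The sensitivity analysis drops very low-Hb subjects, so it serves as a check and does not replace the main analysis.
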